3.1. STUDY MEASURES

[figure not shown]
The outline of the study was presented on session 3.

Initial Visit: Enrolment (Visit 1): Baseline demographic data will be recorded at the time of study enrolment including age, sex, chronic kidney disease (CKD) etiology, Charlson comorbidity index, history of polycystic kidney disease, previous abdominal surgery and presence of hernias, catheter technique placement.

The following anthropometric measurements are required:

- 1) Height: measured standing with shoes off
- 2) Weight: measured with shoes off and “empty” of dialysis fluid. If weighed with fluid in PD the fill volume should be subtracted to give a “dry weight”
- 3) The distance from the decubitus plane to mid-axillary line measured using the method described below:
 - a. The decubitus plane is defined as the bed or couch with the patient lying supine (Figure 2 (A))
 - b. The mid-axillary line is found by:
 - i. The patient raises their arm above the head.
 - ii. Locating the apex of the armpit, the deepest part of the armpit that the hand can reach.
 - iii. The midaxillary line is the line parallel to the ground from the apex of the axilla downward along the lateral chest wall. (Figure 2 (B))
 - iv. A level ruler is used to parallel to the ground to align its midline with the midaxillary line located in the previous step.
 - c. Using another level ruler perpendicular to the ground to measure the distance from the midaxillary line to the decubitus plane

- 4) Waist circumference: measured with a tape measure wrapped above the iliac crests around the level of the umbilicus. See Figure 2 (C).

Created in BioRender.com 

Figure 2 Measurements required to estimate IPP: The patient is placed fully supine on a couch (A). The couch defines the decubitus plane, while the mid-axillary line is identified- the distance between these two planes is measured (B). Waist circumference is measured above the iliac crests at the level of the umbilicus (C).

At Visit 1, 2 and 3 the following information will also be recorded: PD modality, prescribed day and night intra-peritoneal volume, adequacy and peritoneal function using peritoneal equilibration test (PET) data, number of peritonitis episodes, hernias, and leakages developed during PD treatment.

The GSRS will be administered at each Visit 1, 2 and 3 using paper questionnaires. At Visit 1 patients who have started dialysis will be asked to recall symptoms in the month prior to starting dialysis.

The estimated IPP will be assessed at Visit 1 using the equations included in Appendix 2 with the Li formula used for the primary outcome measure.

For the prevalent and incident cohorts. Visit 1 will take place at the time of study enrolment. Visit 2 will take place alongside a routine clinic visits between 60 to 120 days after enrolment (2-4 months). Visit 3 will similarly take place between 320 and 380 days (11-13 months) after study enrolment.

Participants who refuse to fill in the GSRS questionnaire or

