3. STUDY DESIGN

This will be a basic science study involving procedures with human participants. It is a prospective observational study examining a prospective cohort of patients treated with peritoneal dialysis for kidney failure.

This will include two separate cohorts within the study, an incident cohort which will include all patients from the time of PD catheter insertion until 8 weeks after starting PD. A second prevalent cohort will include all patients treated with PD who are greater than 8 weeks from the start of dialysis. Patients will be recruited to either the incident or prevalent cohort.

A minimum of 150 patients will be recruited to both cohorts, so there will be a total of 300 participants.

The study will involve the delivery of two clinical assessments only, the measurements required to estimate IPP and the administration of the gastrointestinal symptom rating scale (GSRS) questionnaire at three time points. Aside from these additional assessments there will be no changes to clinical care and specifically any changes to intra-peritoneal dialysate volume will only be made by the clinical team caring for the patient without reference to the eIPP or GSRS.

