3.2. STUDY OUTCOMES

The primary outcome will be the incidence of non-infectious PD-related complications identified by the clinical team caring for the patient including the development of a new:

- Hernia
- Pleuroperitoneal fistula (PPF)
- Patent processus vaginalis (PPV)
- Retroperitoneal leak

The secondary outcome will be:

- changes in patient reported outcome measures on the GSRS at 3 and 12 months following study recruitment.referral for surgical fixation of non-infectious PD-related complications
- modality change to APD
- transfer to haemodialysis due to the non-infectious complications

During the period of 12 months from study enrolment. Radiological imaging is not required for confirmation nor is surgical fixation.

In Visit 2 and 3, participants who 1) refuse to fill in the GSRS questionnaire, 2) loss of adequate mental capacity to fill in the GSRS questionnaire, 3) refuse to consent clinicians to record their: PD modality, prescribed day and night intra-peritoneal volume, adequacy and peritoneal function using peritoneal equilibration test (PET) data, number of peritonitis episodes, hernias, and leakages developed during PD treatment, 4) defaulted follow-up visits, 5) become pregnant, and 6) received renal transplantation, will be recorded as early withdrawal from the study. Their reason to be withdrawal will be recorded. Data before withdrawal will still be used in outcome analysis. Participants who are withdrawing early from the study will receive same standard and schedule of care.

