4. PARTICIPANT ENTRY

4.1. PRE-REGISTRATION EVALUATIONS

No pre-registration evaluations are required. All patients with kidney failure treated with peritoneal dialysis are eligible.

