7. STATISTICS AND DATA ANALYSIS

7.1. POWER CALCULATION

A small underpowered observational study of measured IPP Castellnaos et al(7), observed an event rate of 36% in a group of patient with high IPP compared with 17% in a group with low IPP. Using these estimates (with alpha of 0.05 with a power of 0.8, including a 0% drop out rate) a minimum of 146 patient will be recruited to the incident cohort. A similar number in the prevalent cohort should confirm any findings.

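### Hernia and leak history is recorded at Visit 1 but not used in the analysis, so the eIPP–complication association can be confounded in a direction the documents do not fix

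*Combined protocol and SAP*

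**What the plan says.** Section 4.1 is open: "All patients with kidney failure treated with peritoneal dialysis are eligible". The two exclusions in Section 4.3 concern allergy to the solution and non-compliance. Neither concerns hernia or leak. The prevalent cohort (Section 3) takes everyone more than 8 weeks from the start of dialysis.

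Section 3.1 expects patients with a history. The baseline list includes "previous abdominal surgery and presence of hernias, catheter technique placement", and Visits 1, 2 and 3 also record hernias and leaks that have arisen on PD. eIPP for the primary analysis is taken at Visit 1, by a formula with one equation for a 2 L fill and another for 1.5 L (appendix of formulas, item 4). On volume, Section 3 says "any changes to intra-peritoneal dialysate volume will only be made by the clinical team caring for the patient", without reference to eIPP or GSRS.

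The primary outcome in Section 3.2 is the incidence of complications "identified by the clinical team caring for the patient including the development of a new" hernia, pleuroperitoneal fistula, patent processus vaginalis or retroperitoneal leak, over 12 months from enrolment. The Study Summary instead counts complications from the time the catheter was inserted. Sections 7.2–7.3 offer descriptive statistics and name no stratum, covariate or restriction. Section 7.1 gives the prevalent cohort the task of confirming the incident finding.

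**The concern.** In a patient with an earlier hernia or leak, that history can act on both sides of the comparison. It can change the chance of a further event whatever the pressure. It can also change the exposure: if the volume was altered after the first event, Visit 1 eIPP is partly a consequence of a complication.

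The word *new* in Section 3.2 limits which events count. It does not separate patients by history, and it does not protect an eIPP measured after the earlier event.

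At stake is the reading of the main association, above all in the prevalent cohort, where earlier events on PD have had time to accumulate. If the two cohorts disagree, the planned analysis cannot show whether pressure or case mix is the reason.

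**Working it through.** **1. The plan's own figure.** Section 7.1 reports that a study of measured IPP "observed an event rate of 36% in a group of patient with high IPP compared with 17% in a group with low IPP", and derives ("with alpha of 0.05 with a power of 0.8, including a 0% drop out rate") that "a minimum of 146 patient will be recruited to the incident cohort". With two equal groups, n per group = [z_α√(2p̄q̄) + z_β√(p₁q₁ + p₂q₂)]² / (p₁ − p₂)², where p̄ = 0.265, √(2p̄q̄) = 0.624, √(p₁q₁ + p₂q₂) = 0.610 and p₁ − p₂ = 0.19.

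- Two-sided: (1.960 × 0.624 + 0.842 × 0.610)² / 0.0361 = 83.5, so 84 per group and 168 in total.
- One-sided: (1.645 × 0.624 + 0.842 × 0.610)² / 0.0361 = 65.7, so 66 per group and 132 in total.

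The 146 is not reproduced from its stated inputs, which is a separate matter. What is needed here is the 36% vs 17% contrast (19 points) and the two-sided power with the planned 150 per cohort: (0.19√75 − 1.223) / 0.610 = 0.69, or 75.6%.

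**2. Does a volume change move eIPP?** The 1.5 L equation minus the 2 L equation is 0.025 × waist + 0.057 × distance − 4.486. The unit of distance is not stated; cm is assumed. At distance 10 cm the change is −2.04 (waist 75 cm), −1.54 (95 cm) and −1.04 (115 cm). Over waist 75–130 cm and distance 8–15 cm the fall is 0.38 to 2.15.

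With assumed waist of mean 95, SD 13 and distance of mean 11.5, SD 1.5, the mean fall is 4.486 − 2.375 − 0.656 = 1.46. The between-patient SD is √((0.193 × 13)² + (0.907 × 1.5)²) = 2.85. The shift is about half an SD, enough to carry some patients across a high/low cut.

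**3. A hand-checkable example.** Assume that 20% have a prior event, split high:low as 36:17 (0.136 and 0.064 of the cohort), that their risk is doubled, and that event-free patients are 0.40 in each group. The event-free contrast is 19 points throughout.

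- No volumes changed: high (0.40 × 0.36 + 0.136 × 0.72) / 0.536 = 45.1%; low (0.40 × 0.17 + 0.064 × 0.34) / 0.464 = 19.3%. Difference **25.8** points.
- Half of the high-group prior patients cross to low and keep their risk: high (0.144 + 0.068 × 0.72) / 0.468 = 41.2%; low (0.068 + 0.068 × 0.72 + 0.064 × 0.34) / 0.532 = 26.1%. Difference **15.2** points; power with 150 is 50%.
- Half cross and their risk falls with the volume: low (0.068 + 0.132 × 0.34) / 0.532 = 21.2%. Difference **20.0** points; power 76%.

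The same history can inflate, dilute or barely alter the result.

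**4. The same question run through the formula.** This is a simulation with the anthropometry above, a median split of eIPP (the plan states no cut), 15–25% with a prior event in the 36:17 ratio, and a risk multiplier of 1.5–2.5.

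| Assumption for prior-event patients | Pooled difference (points) | Event-free difference (points) |
|---|---|---|
| All moved from 2 L to 1.5 L; one flat risk, 0.265 × multiplier | 12–15 | 17–18 |
| All moved; multiplier on risk at their natural pressure | 17–20 | 17–18 |
| All moved; multiplier on risk at their current pressure | 19–23 | 17–18 |
| None moved; flat risk | 17–21 | 19 |
| None moved; multiplier on own risk | 22–33 | 19 |

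In the second row the difference looks intact, yet the risk ratio falls from 2.1 (0.36/0.17) to 1.7–1.9. No row reverses the sign.

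**5. Cost of restricting instead.** If 10, 20 or 30% have a prior event, 135, 120 or 105 of 150 remain event-free, and two-sided power falls from 75.6% to 71.0, 65.8 or 59.9%.

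**The case against.** A reader might infer that pooling must pull the association toward zero, to some 12–15 points, or even reverse it. The documents do not support that. The 12–15 points arise only when every prior-event patient has been moved to 1.5 L and all carry one flat risk unrelated to pressure. The flat risk does most of the work: the result hardly depends on the multiplier. Nor does a lower volume place these patients as a group in the low half: with all of them moved, 47–50% still lie above the median.

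The causal links are also not in the documents. Nothing says that a complication leads to a lower prescribed volume or raises the risk of a second event. The Section 3 sentence on volume concerns changes during the study, not earlier ones. Nor is it stated whether the day or night volume selects the equation. If one equation served everyone, the volume route would close, though confounding by history would remain.

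Three further points are fair. *New* and the 12-month window in Section 3.2 keep old events out of the outcome, but the Study Summary contradicts that window. The incident cohort, the only one with a sample-size calculation, is less exposed, though a pre-existing hernia can occur there too. And if the aim is purely predictive, eIPP as found at Visit 1 is a legitimate exposure. Even then the reader needs to know whether it adds anything to a history that is already known.

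Finally, the analysis section uses no baseline variable at all, so this is one case of a wider gap. It merits its own line because this variable is the earlier form of the outcome itself and can also alter the exposure.

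**Conclusion.** The point stands as one about possible confounding, not about a known bias. The text confirms open eligibility, a recorded but unused history, a single eIPP taken after any earlier event, and a formula that depends on volume. Direction and size are not derivable. Under the assumed inputs in the table the pooled difference spans about 12 to 33 points, against 17–19 in event-free patients, and the documents do not say where in that span the study lies. The span rests on assumed prior-event shares, risk multipliers, volume changes, anthropometry and a median cut. Attenuation of a given size, or reversal, should not be claimed. The effect would fall mainly on the prevalent cohort.

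**What to change.** In Section 7.2, keep all participants. In each cohort, report the eIPP–complication association stratified by, or adjusted for, hernia or leak present at Visit 1 or recorded on PD before it. Show the event-free stratum separately as a sensitivity analysis: there, eIPP cannot reflect a volume change made because of an earlier hernia or leak.

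In Section 3.2, state what counts as *new* in a patient who already has a hernia or leak (for example recurrence, enlargement or another site), and reconcile the 12-month window with the Study Summary's count from catheter insertion.

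The variables are already collected at Visit 1, so no data collection changes. The cost is slightly more analysis and less precise stratum estimates: at 10–30% with a history, the prior-event stratum holds only 15–45 of 150. Do not make the event-free set the primary one. That would lose the power shown in step 5 and narrow the study's stated population of all adult incident and prevalent patients.

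### Section 3.1 does not secure a current-symptom GSRS at Visit 1 for patients already on dialysis, and section 3.2 does not name the baseline for GSRS change

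*Combined protocol and SAP*

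**What the plan says.** Section 3 (Study design) describes "the administration of the gastrointestinal symptom rating scale (GSRS) questionnaire at three time points". On numbers it says "A minimum of 150 patients will be recruited to both cohorts, so there will be a total of 300 participants".

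Section 3.1 (Study measures) repeats the schedule: "The GSRS will be administered at each Visit 1, 2 and 3 using paper questionnaires". The next sentence adds an instruction for a subgroup: "At Visit 1 patients who have started dialysis will be asked to recall symptoms in the month prior to starting dialysis". Later in the same section, "The estimated IPP will be assessed at Visit 1" and "Visit 1 will take place at the time of study enrolment". Visit 2 follows 60 to 120 days after enrolment and Visit 3 follows 320 to 380 days after.

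Section 3.2 (Study outcomes) lists as a secondary outcome "changes in patient reported outcome measures on the GSRS at 3 and 12 months following study recruitment". Section 7 plans descriptive statistics only and defines no change score. The secondary objective in section 2 is the relationship of eIPP with patient-reported outcomes, gastrointestinal symptoms in particular.

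**The concern.** A change score needs a defined starting value. For patients not yet on dialysis at Visit 1 there is only one candidate, their symptoms at enrolment. For patients already on dialysis, the only Visit 1 instruction specific to them points to an earlier period, and nothing guarantees that their present symptoms are also recorded.

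Two things are at stake. The first is data: if only the recall is collected, no symptom score sits alongside the eIPP taken at the same visit, and no later analysis can supply it. The second is meaning: change from a recalled pre-dialysis state combines the effect of starting dialysis, a variable elapsed time and recall error with whatever happened after recruitment. Sites that read the sentence differently would also return Visit 1 scores that cannot be pooled.

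**Working it through.** **Side-by-side reading.** No published figure is to be reproduced here; the question is what the text fixes.

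| Reading | What exists at Visit 1 for patients on dialysis | What is left open |
|---|---|---|
| Recall replaces the current form | Recalled pre-dialysis score only | No score concurrent with eIPP; change runs from before dialysis |
| Recall is added | Recalled and current scores | Section 3.2 does not say which is the baseline |

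The count of three time points in section 3 does not decide between them. Two reference periods completed at Visit 1 still make one time point.

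**How the two change scores differ.** Let F be the follow-up score, C the current score at Visit 1 and R the recalled score. Then

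F − R = (F − C) + (C − R).

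The two versions differ by C − R, the reported change between the pre-dialysis month and enrolment. The documents give no GSRS mean, SD or correlation, so this term cannot be sized and no effect on bias or precision is claimed.

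**Who falls under the instruction (planned numbers, section 3).**
- Prevalent cohort: more than 8 weeks from the start of dialysis by definition, so all 150.
- Incident cohort: from catheter insertion to 8 weeks after starting PD, so 0 to 150. The split is not given.
- Total: 150 + 0 = 150 to 150 + 150 = 300 of 300, that is 50% to 100%.

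**Elapsed time from the end of the recalled month (the start of dialysis) to follow-up.** 8 weeks = 56 days. Start of dialysis is taken to mean the same thing in sections 3 and 3.1.

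| Group | Visit 2 (days) | Visit 3 (days) |
|---|---|---|
| Nominal, from enrolment | 60 to 120 | 320 to 380 |
| Prevalent | more than 56 + 60 = 116, no upper limit | more than 56 + 320 = 376, no upper limit |
| Incident, already on PD | 0 + 60 = 60 to 56 + 120 = 176 | 0 + 320 = 320 to 56 + 380 = 436 |

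The incident row assumes that starting dialysis means starting PD. If earlier haemodialysis counts, the 56-day cap no longer applies and the intervals run from 60 and from 320 days without an upper limit. The prevalent rows have no ceiling because neither section 3 nor the eligibility criteria limit time on dialysis.

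**The case against.** The strongest reply is that section 3.1 first sets a rule for everyone, a GSRS at each visit, and then adds an instruction for some, without any word such as instead. On that reading the current form is already collected, and all that is missing is a baseline label, which can be supplied before analysis with no data lost. This is a fair reading, at least as natural as replacement. It does not dispose of the point: the text does not state it, a site can reasonably do otherwise, and the baseline would still be unnamed.

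A second reply is that a pre-dialysis anchor may be deliberate. It would put patients on dialysis on a similar footing to incident patients enrolled before dialysis, and in prevalent patients current symptoms may already reflect intraperitoneal pressure. That stands as a reason to keep the recalled score, but not as a reason to go without the current one.

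A third is that the study figures and the GSRS form are not visible here, and a visit schedule might settle the matter. That also stands as a limit. A reference period printed on the form alone would still not say whether the recall replaces the current form or adds to it.

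Two stronger inferences should be resisted. A reader might take the three time points as showing that the recall replaces the current form; the phrase fits both readings. A reader might also say that a pre-dialysis baseline contradicts section 3.2. That section gives the times of assessment and names no baseline, so it does not clearly rule one out.

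**Conclusion.** The point holds as a gap in the text with a potentially irrecoverable consequence. The protocol permits collection of only a recalled pre-dialysis score at Visit 1 in 150 to 300 of the planned 300 participants. If that happens, none of them has a symptom score concurrent with eIPP, and their change score starts at a time with no upper limit in the prevalent cohort. If both scores are collected, nobody lacks a current score, but the same 150 to 300 people have two candidate baselines.

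The range counts people covered by the instruction, not people known to lack a score. It rests on the planned 150 per cohort and on the unknown share of incident patients already on dialysis at enrolment.

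The reach is limited. A reader might infer that the secondary objective fails; it does not, because associations of Visit 1 eIPP with GSRS at Visits 2 and 3 remain estimable under either reading. The primary outcome is untouched, and the planned analysis is descriptive. This is a cheap improvement, best made before further Visit 1 assessments take place.

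**What to change.** - **Section 3.1, with matching wording in section 3:** state that every participant completes a current-symptom GSRS at Visit 1, with the same reference period as at Visits 2 and 3. State that patients already on dialysis also complete the pre-dialysis recall as a separately labelled score. The same edit can say whether starting dialysis means PD or any dialysis.
- **Section 3.2:** name the current-symptom Visit 1 score as the baseline for change after recruitment, and report change from the recalled score separately, by cohort. Both contrasts are then kept.

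The cost is a minor protocol wording change and one extra short paper form at Visit 1 for 150 to 300 participants, or none if the recall is already additional. Section 8.1 records that ethics approval has been obtained, so the sponsor should check whether the extra form needs approval as a change. One limitation remains: current-symptom baselines in the incident cohort will mix patients before and after starting dialysis. Splitting that cohort by dialysis status at Visit 1 is optional and not needed to close the gap.

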3.2. STUDY OUTCOMES

The primary outcome will be the incidence of non-infectious PD-related complications identified by the clinical team caring for the patient including the development of a new:

- Hernia
- Pleuroperitoneal fistula (PPF)
- Patent processus vaginalis (PPV)
- Retroperitoneal leak

The secondary outcome will be:

- changes in patient reported outcome measures on the GSRS at 3 and 12 months following study recruitment.referral for surgical fixation of non-infectious PD-related complications
- modality change to APD
- transfer to haemodialysis due to the non-infectious complications

During the period of 12 months from study enrolment. Radiological imaging is not required for confirmation nor is surgical fixation.

In Visit 2 and 3, participants who 1) refuse to fill in the GSRS questionnaire, 2) loss of adequate mental capacity to fill in the GSRS questionnaire, 3) refuse to consent clinicians to record their: PD modality, prescribed day and night intra-peritoneal volume, adequacy and peritoneal function using peritoneal equilibration test (PET) data, number of peritonitis episodes, hernias, and leakages developed during PD treatment, 4) defaulted follow-up visits, 5) become pregnant, and 6) received renal transplantation, will be recorded as early withdrawal from the study. Their reason to be withdrawal will be recorded. Data before withdrawal will still be used in outcome analysis. Participants who are withdrawing early from the study will receive same standard and schedule of care.

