6. ASSESSMENT AND FOLLOW-UP

All candidates will be followed up for 12 months following initial eIPP measurement. The formal end of this study will be 12 months after the eIPP measurement of the 150th incident cohort patient. No further recruitment to the prevalent cohort group will take place after the recruitment of the 150th incident patient. Incidental findings will not be recorded and reported in this study. Only the outcome mentioned in Section 3.2 will be recorded and analysed. Participants will be advised to report incidental findings to their GP and clinical care team as per local guidelines or standard of care.

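### The plan does not keep eIPP from the treating team that identifies the primary outcome, so detection of complications could differ by eIPP and bias the main association

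*Combined protocol and SAP*

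**What the plan says.** Section 3.2 defines the primary outcome as new hernia, pleuroperitoneal fistula, patent processus vaginalis or retroperitoneal leak "identified by the clinical team caring for the patient". On confirmation it says: "Radiological imaging is not required for confirmation nor is surgical fixation". The protocol gives no case definitions, no masked review of events and no standard examination for complications.

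The exposure comes first. Section 3.1 says "The estimated IPP will be assessed at Visit 1", and Section 6 says "All candidates will be followed up for 12 months following initial eIPP measurement". Section 3.1 also says "Visit 2 will take place alongside a routine clinic visits", with Visit 3 arranged in a similar way. Hernias and leakages are recorded at these visits.

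Section 3 has two relevant statements. The general one is "Aside from these additional assessments there will be no changes to clinical care". The specific one is that changes in dialysate volume "will only be made by the clinical team caring for the patient without reference to the eIPP or GSRS". Neither says who calculates eIPP, where it is recorded, or whether the treating team sees it.

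Section 7 plans descriptive statistics only. It includes no analysis of how outcomes were ascertained.

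**The concern.** The primary objective is the association between eIPP and complications. For that association to be interpretable, the chance that a complication is noticed and recorded should not depend on eIPP. Here the people who decide that an event has occurred are the treating clinicians, no objective confirmation is needed, and the protocol leaves open whether they know the exposure.

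Section 1.2 itself states that high IPP is related to hernias and peritoneal leak. A clinician who sees a high value therefore has a reason, given in the protocol, to examine more closely. The primary formula in Appendix 1 is simple arithmetic on waist and one distance, so a value can be produced at the bedside unless the protocol prevents it.

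If detection differed by eIPP, an association could appear where none exists, or a real one could be distorted. Recruiting more patients would not correct this. Three of the secondary outcomes (surgical referral, change to APD and transfer to haemodialysis) are clinical decisions or follow from them, so they share the weakness.

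**Working it through.** **Step 1: what is restricted.**

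| Question | What the protocol says | Where |
|---|---|---|
| When is eIPP obtained? | Visit 1, before the outcome window | 3.1 |
| Who identifies events? | Treating team | 3.2 |
| Is confirmation required? | No | 3.2 |
| May eIPP guide volume changes? | No | 3 |
| May eIPP otherwise alter care? | Care is said to be unchanged | 3 |
| Who calculates or sees eIPP? | Not stated | – |
| Are assessors masked, or events adjudicated? | Not stated | – |

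Use of eIPP is restricted, but access to it is not.

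**Step 2: inputs for an illustration.** Section 7.1 gives event rates of 36% (high IPP) and 17% (low IPP), alpha 0.05, power 0.8 and a minimum of 146 incident patients. I take:
- a common true risk of (36% + 17%)/2 = 26.5%;
- an even split of 146/2 = 73 per group.

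The equal risk, the even split and the detection ratios below are my assumptions.

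The plan's 146 is not reproduced by the usual formula. With two-sided alpha and equal groups,

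n = [1.96·√(2·0.265·0.735) + 0.842·√(0.36·0.64 + 0.17·0.83)]² / 0.19² = 83.5, so 84 per group or 168 in all.

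The one-sided version gives 132. That is a separate matter. Here 146 serves only to set a realistic group size.

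**Step 3: effect of unequal detection.** Let detection be complete at high eIPP and a fraction s as good at low eIPP. The observed risks are p and s·p, so the observed risk ratio is 1/s when the true ratio is 1.

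The chance of a significant result is that of a two-sided pooled test of two proportions at 5%. The plan specifies no test; I use this one because Section 7.1 is framed as a comparison of two proportions. For s = 0.8:
- observed risks 0.265 and 0.212, difference 0.053, mean 0.2385;
- null SE = √(0.2385·0.7615·2/73) = 0.0705;
- actual SE = √[(0.265·0.735 + 0.212·0.788)/73] = 0.0704;
- Φ[(0.053 − 1.96·0.0705)/0.0704] + Φ[(−0.053 − 1.96·0.0705)/0.0704] = Φ(−1.21) + Φ(−2.72) = 0.113 + 0.003 = 11.6%.

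| Relative detection s | Observed risks | Observed risk ratio | False-positive rate |
|---|---|---|---|
| 1.0 | 26.5% vs 26.5% | 1.00 | 5.0% |
| 0.9 | 26.5% vs 23.85% | 1.11 | 6.6% |
| 0.8 | 26.5% vs 21.2% | 1.25 | 11.6% |
| 0.7 | 26.5% vs 18.55% | 1.43 | 20.9% |

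**Step 4: sensitivity to the inputs.**
- At s = 0.8 the false-positive rate is 8.8% if the true risk is 17%, and 15.3% if it is 36%.
- With 150 per group (both cohorts together, split evenly), a true risk of 26.5% and s = 0.8, it rises to 18.9%. A larger sample makes a biased difference easier to declare significant.
- To produce the whole 36% versus 17% contrast with no true effect, s would have to be 17/36 = 0.47.

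**The case against.** The strongest reply is that the mechanism is assumed. A reader might infer that the treating team is shown eIPP and acts on it. The documents do not support that: they do not say that eIPP is reported to the team or entered in the clinical record, and they define no cut-off for a high value. This stands, and it limits the point to one about access that is left open.

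A second reply is that volume changes are not the only protected area. The sentence in Section 3 starts with a general commitment to unchanged care, and examining high-eIPP patients more closely would arguably breach it. That is fair, but only a partial answer. Closer attention to a patient with a known high value need not be a deliberate change of care, and the commitment does not govern who holds the value.

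Third, not requiring imaging or surgery is a reasonable pragmatic choice in an unfunded observational study. Lack of confirmation does not by itself make errors depend on eIPP. A reader might also infer that most events are diagnosed on examination alone, or that eIPP is measured again at the follow-up clinics. Section 3.2 does not say how often imaging is used. Section 3.1 places the anthropometry and eIPP at Visit 1; only the ambiguous mention of three time points in Section 3 could suggest otherwise.

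Finally, masking the number does not hide waist or build, and waist is the positive term in the primary formula. The proposed masking is therefore incomplete.

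**Conclusion.** The point holds as a correctable gap in design. An unconfirmed outcome is identified by clinicians after the exposure has been assessed, and nothing keeps the exposure value from them. Detection could therefore differ by eIPP and bias the primary association.

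Neither the size nor the direction can be derived from the documents. Under the stated assumptions, relative detection of 0.9 to 0.7 gives a spurious risk ratio of 1.11 to 1.43 and a false-positive rate of 6.6% to 20.9%. These figures show what modest differences in detection would do; they do not predict what will happen.

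It would go too far to say that detection bias alone could readily produce the planning contrast of 36/17 = 2.12. That would need fewer than half of the events at low eIPP to be found, relative to high eIPP.

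The point should be settled before data accrue. Masking cannot be applied afterwards, and the basis of a diagnosis is harder to recover later.

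**What to change.** 1. **Amend Section 3.1.** For eIPP, sites record only the raw formula inputs at Visit 1: waist, decubitus-plane to mid-axillary distance, height, weight and fill volume, plus the Charlson index, PD duration and daily ultrafiltration that the other Appendix 1 formulas need. Fill volume is essential because it selects the version of the primary formula. Section 3.1 does not currently name PD duration or daily ultrafiltration among the items recorded. All other planned data are collected as now.
2. **Calculate eIPP centrally**, after each participant's 12-month outcome has been entered, and keep it out of the clinical record. This changes the present statement that eIPP is assessed at Visit 1, so that sentence must be reworded.
3. **Add one form field** for how each event was identified: clinical, imaging or surgery. The outcome definition stays as it is and no extra imaging is requested.
4. **Add to Section 7** a sensitivity analysis limited to events confirmed by imaging or surgery. State its limit: clinicians choose whom to image or refer, so it may share some of the bias.

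The cost is a few sentences, the form field for the basis of diagnosis, and fields for any formula inputs not yet collected. No visit, assessor or scan is added. The price is that eIPP is unavailable during follow-up, which fits Section 3, where volume decisions may not refer to it anyway. Visible waist and body habitus remain, and the report should say so.
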